6.1.2 Dose Stopping Safety Criteria

6.1.2.1 Liver Chemistry Stopping Criteria

Dabrafenib will be stopped if any one of the following criteria is met:

- ALT ≥ 3 times (x) upper limit of normal (ULN) and bilirubin ≥ 2 x ULN (Serum bilirubin fractionation should be performed if testing is available. If testing is unavailable, record presence of detectable urinary bilirubin on dipstick indicating direct bilirubin elevations and suggesting liver injury)
- ALT ≥ 5 x ULN
- ALT ≥ 3 x ULN if associated with the appearance or worsening of rash or hepatitis symptoms (fatigue, nausea, vomiting, right upper quadrant pain or tenderness, fever, rash or eosinophilia)
- ALT ≥ 3 x ULN and persists for ≥ 4 weeks

- ALT \geq 3 x ULN and cannot be monitored weekly for \geq 4 weeks

Patients with ALT \geq 3 x ULN and <5 x ULN and bilirubin < 2 x ULN, and who do not have hepatitis symptoms or rash, can continue study drug Dabrafenib as long as liver enzymes can be monitored weekly for 4 weeks.

When any of the liver chemistry stopping criteria 1-5 is met, do the following:

- Immediately withdraw investigational product for that subject
- Report the event within 24 hours of learning its occurrence
- Complete the liver event CRF and SAE data collection tool if the event also meets the criteria for an SAE. All events of ALT \geq 3xULN and bilirubin \geq 2xULN ($>35\%$ direct bilirubin) (or ALT \geq 3xULN and INR >1.5 , if INR measured; INR measurement is not required and the threshold value stated will not apply to patients receiving anticoagulants), termed 'Hy's Law', must be reported as an SAE (excluding studies of hepatic impairment or cirrhosis).

NOTE: If serum bilirubin fractionation is not immediately available, withdraw study drug for that subject if ALT \geq 3xULN and bilirubin \geq 2xULN. Serum bilirubin fractionation should be performed if testing is available. If testing is unavailable, record presence of detectable urinary bilirubin on dipstick, indicating direct bilirubin elevations and suggesting liver injury.

- Complete the liver imaging and/or liver biopsy CRFs if these tests are performed
- Perform liver event follow up assessments, and monitor the subject until liver chemistries resolve, stabilize, or return to baseline values as described below.
- Withdraw the subject from the study (unless further safety follow up is required) after completion of the liver chemistry monitoring as described below.
- Do not re-challenge with investigational product.

In addition, for criterion 1:

- Make every reasonable attempt to have subjects return to clinic within **24 hours** for repeat liver chemistries, liver event follow up assessments (see below), and close monitoring
- A specialist or hepatology consultation is recommended
- Monitor subjects twice weekly until liver chemistries (ALT, AST, alkaline phosphatase, bilirubin) resolve, stabilize or return to within baseline values for criteria 2, 3, 4 and 5:
- Make every reasonable attempt to have subjects return to clinic **within 24-72 hrs** for repeat liver chemistries and liver event follow up assessments (see below)
- Monitor subjects weekly until liver chemistries (ALT, AST, alkaline phosphatase, bilirubin) resolve, stabilize or return to within baseline values; criterion 5 subjects should be monitored as frequently as possible.

Subjects with ALT \geq 3xULN **but** <5 xULN **and** bilirubin <2 xULN, without hepatitis symptoms or rash, and who can be monitored weekly for 4 weeks

- Notify within 24 hours of learning of the abnormality to discuss subject safety.
- Can continue investigational product must return weekly for repeat liver chemistries

(ALT, AST, alkaline phosphatase, bilirubin) until they resolve, stabilize or return to within baseline)

- If at any time these subjects meet the liver chemistry stopping criteria, proceed as described above
- If, after 4 weeks of monitoring, ALT <3xULN and bilirubin <2xULN, monitor subjects twice monthly until liver chemistries normalize or return to within baseline values.

For criteria 1-5, make every attempt to carry out the liver event follow up assessments described below:

- Viral hepatitis serology including:
- Hepatitis A IgM antibody;
- Hepatitis B surface antigen and Hepatitis B Core Antibody (IgM);
- Hepatitis C RNA;
- Cytomegalovirus IgM antibody;
- Epstein-Barr viral capsid antigen IgM antibody (or if unavailable, obtain heterophile antibody or monospot testing);
- Hepatitis E IgM antibody
- Blood sample for pharmacokinetic (PK) analysis, obtained within 24 hours of last dose. Record the date/time of the PK blood sample draw and the date/time of the last dose of investigational product prior to blood sample draw on the CRF. If the date or time of the last dose is unclear, provide the subject's best approximation. If the date/time of the last dose cannot be approximated OR a PK sample cannot be collected in the time period indicated above, do not obtain a PK sample. Instructions for sample handling and shipping are in the SPM
- Serum creatine phosphokinase (CPK) and lactate dehydrogenase (LDH).
- Fractionate bilirubin, if total bilirubin \geq 2xULN
- Obtain complete blood count with differential to assess eosinophilia
- Record the appearance or worsening of clinical symptoms of hepatitis, or hypersensitivity, such as fatigue, nausea, vomiting, right upper quadrant pain or tenderness, fever rash or eosinophilia as relevant on the AE report form
- Record use of concomitant medications, acetaminophen, herbal remedies, and other over the counter medications, or putative hepatotoxins, on the concomitant medications report form.
- Record alcohol use on the liver event alcohol intake case report form

The following are required for subjects with ALT \geq 3xULN and bilirubin \geq 2xULN

(>35% direct) but are optional for other abnormal liver chemistries:

- Anti-nuclear antibody, anti-smooth muscle antibody, Type 1 anti-liver kidney microsomal antibodies, and quantitative total immunoglobulin G (IgG or gamma globulins).
- Serum acetaminophen adduct HPLC assay (quantifies potential acetaminophen contribution to liver injury in subjects with definite or likely acetaminophen use in the preceding week (James LP. Drug Metab Disp 2009; 37:1779–1784).
- Liver imaging (ultrasound, magnetic resonance, or computerized tomography) to evaluate liver disease.

6.1.2.2 Left Ventricular Ejection Fraction (LVEF) Stopping Criteria

ECHO or MUGA must be performed at baseline and at follow-up visit(s) per the schedule in the Study Calendar. Subjects who have an asymptomatic, absolute decrease of > 10% in LVEF compared to baseline and the ejection fraction is below the institution's lower limit of normal (LLN) should temporarily discontinue Dabrafenib and have a repeat evaluation of LVEF within 1 week. ECHO or MUGA should be repeated every 1-2 weeks for 4 weeks or until LVEF recovery to above institutional lower limit of normal and within 10% of baseline

If the LVEF recovers (defined as \geq LLN and absolute decrease \leq 10% compared to baseline) at any time during the next 4 weeks, the subject may be restarted on Dabrafenib at reduced dose level, after consultation and approval of the Protocol Chair. For such subjects, monitoring of LVEF will then be performed 2 and 4 weeks after rechallenge, and every 4 weeks thereafter for 12 weeks and then per protocol.

If repeat LVEF does not recover within 4 weeks, then the subject should permanently discontinue Dabrafenib. Ejection fraction should continue to be monitored every 4 weeks for 16 weeks or until resolution.

Subjects with a Grade 3 or 4 (symptomatic) left ventricular systolic dysfunction must discontinue Dabrafenib. Ejection fraction should continue to be monitored every 4 weeks for 16 weeks or until resolution. If recovery occurs (LVEF to above institutional LLN and symptom resolution) within 4 weeks, the subject may restart Dabrafenib at a reduced dose after consultation and approval of the Protocol Chair.

6.1.2.3 Valvular Toxicity Stopping Criteria

Subjects who have an asymptomatic, moderate regurgitation or stenosis by ECHO (Grade 2 mitral/tricuspid/aortic valvular toxicity per CTC AE v4.0) should temporarily discontinue Dabrafenib and have a repeat evaluation by ECHO within 1 week. ECHO should be repeated every 1-2 weeks for 4 weeks or until valve recovery to baseline.

If the valve recovers to baseline any time during the next 4 weeks, the subject may be restarted on Dabrafenib at a reduced dose(s). For such subjects, monitoring of the valve via ECHO will then be performed 2 and 4 weeks after rechallenge, and every 4 weeks thereafter for 12 weeks and then per protocol

If repeat ECHO does not reveal valve recovery to baseline within 4 weeks, then the subject should permanently discontinue Dabrafenib. The valve should continue to be monitored via ECHO every 4 weeks for 16 weeks or until resolution.

Subjects with a Grade 3 or 4 valvular toxicity (symptomatic, severe regurgitation/stenosis by imaging, with symptoms controlled by medical intervention) must discontinue Dabrafenib. Valvular toxicity should continue to be monitored every 4 weeks for 16 weeks or until resolution. If recovery occurs (return to baseline via imaging AND symptom resolution) within 4 weeks, the

subject may restart Dabrafenib at a reduced dose after consultation and approval of the Protocol Chair.

6.1.2.4 QTc Stopping Criteria

If QTc corrected (QTcB) is greater than or equal to 530 milliseconds¹, the study drug Dabrafenib will be held.

¹ If ECG demonstrates greater than 500 millisecond QTc (grade 3 or 4), obtain 2 more ECGs over a brief period, and then use the averaged QTc values of the 3 ECGs to determine if averaged QTc greater than or equal to 530 millisecond. If that is the case, the subjects should have study medication withheld.

If the QTc prolongation resolves to Grade 1 or baseline, the subject may be restarted on the study medication if after the Protocol Chair agrees that the subject will benefit from further treatment.

6.2 Trametinib Delays/Modifications (applicable to patients on ARM B):

Given that there are several overlapping AEs between Dabrafenib and Trametinib, dose modification/stopping guidelines for all patients on ARM B must follow guidelines for Dabrafenib. In each of those categories, dose reduction, dose holding or dose continuation of Trametinib must follow similar criteria as for Dabrafenib. If there is discrepancy between two guidelines for a given AE, please follow guidelines for Dabrafenib for patients on ARM B. Diarrheas, peripheral/periorbital edema, acneiform rash, please follow guidelines given in section 6.2.

Table 8. Trametinib Dose Levels

| Dose Level | Trametinib Dose |
|-------------------|------------------------|
| 0 | 2 mg once a day |
| - 1 | 1.5 mg once a day |
| - 2 | 1 mg once a day |

A maximum of two Trametinib dose level reductions are allowed. If a third dose level reduction is required, treatment will be permanently discontinued. If a dose reduction of Trametinib is required, but the toxicity resolves and no additional toxicities are seen after two cycles of treatment, the dose of Trametinib may be re-escalated but should not exceed 2 mg once a day.

Trametinib dose modification guidelines are outlined in Table 9 for clinically significant toxicities that are deemed related to Trametinib (i.e. peripheral and periorbital edema).

Dose modification guidelines for rash are outlined in Table 10.

Table 9. Dose Delay and Modification for Trametinib related AEs (for peripheral edema, periorbital edema)

| Toxicity Grade^a | Dose Modification of Trametinib |
|-----------------------------------|--|
| Grade 1 | Continue at current dose level. |
| Grade 2 | Interrupt treatment until toxicity resolves to Grade 1 or baseline. Upon resolution, restart treatment at current dose level with supportive care as clinically indicated. Consider dose reduction by at least one dose level. |
| Grade 3 | Interrupt treatment until toxicity resolves to Grade 1 or baseline. Upon resolution, consider dose reduction by at least one dose level. |
| Grade 4 | Permanently discontinue Trametinib |

Treatment with Trametinib may be interrupted for up to 21 days to allow resolution of toxicity, or based on investigator discretion. If the investigator concludes that continued treatment will benefit a subject who has experienced a treatment delay >21 days, then the subject may continue Trametinib therapy.

Table 10. Dose Modification Rash Management Guidelines for Trametinib

| Step | Rash grading | Rash severity | Management of Rash | Trametinib Dose Adjustment |
|-------------|---------------------|---|--|--|
| 1 | Mild | Localized Minimally symptomatic No impact on ADL No sign of superinfection | Initiate prophylactic regimen if not already started. Consider using moderate strength topical steroid.* Reassess after 2 weeks; if rash worsens or does not improve, proceed to step 2 | Continue current dose. Reassess after 2 weeks; if rash worsens or does not improve, proceed to step 2 |
| 2 | Moderate | Generalized Mild symptoms (eg, pruritis, tenderness) Minimal impact on ADL No sign of superinfection | Initiate prophylactic regimen if not already started, using moderate strength topical steroid.* Reassess after 2 weeks; if rash worsens or does not improve, proceed to step 3 | Reduce dose by at least one dose level or consider interrupting treatment until resolution to Grade 1. If toxicity resolves, can consider re-escalation to initial dose level. Reassess after 2 weeks; if rash worsens or does not improve, proceed to step 3 |
| 3 | Severe | Generalized Severe symptoms (e.g., pruritis, tenderness) Significant impact on ADL Sign of or potential for superinfection | Initiate prophylactic regimen if not already started, using moderate strength topical steroids PLUS methylprednisolone dose pack. Consider obtaining dermatology consultation. Manage rash per dermatologist's recommendation. | Interrupt treatment until rash improves (moderate, mild) or resolves, then follow steps outlined for the appropriate grading. Reassess after 2 weeks; if rash worsens or does not improve, permanently discontinue treatment with Trametinib. |

*e.g., hydrocortisone 2.5% cream or fluticasone propionate 0.5% cream

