6.1.1 Guidelines for Dabrafenib Dose Modification and Treatment of Adverse Events

The severity of adverse events will be graded utilizing the Common Terminology Criteria for Adverse Events Version 4.0 (CTCAE v4.0). Dose modifications of Dabrafenib will be made according to the dose levels outlined in **Table 1**.

Table 1. Dabrafenib Dose Levels

| Dose Level | Dabrafenib Dose/Schedule |
|-------------------|---------------------------------|
| 0 | 150 mg BID |
| - 1 | 100 mg BID |
| - 2 | 75 mg BID |
| - 3 | 50 mg BID |

Guidelines for dose modifications and interruptions for management of toxicities associated with the study treatment other than those pertaining to neutropenia, fever, rash, hand foot skin reactions (HFSR), renal insufficiency, liver chemistry abnormalities, left ventricular ejection fraction (LVEF) are provided in **Table 2**.

Dose modifications specifically for neutropenia are outlined in **Table 3**. Prophylactic antibiotics are recommended for treatment of neutropenic fever (defined as a single fever $>38.3^{\circ}\text{C}$ (101°F), or a sustained temperature $>38^{\circ}\text{C}$ (100.4°F) for more than one hour in a patient with absolute neutrophil count (ANC) <500 cells/microL, or <1000 cells/microL with a predicted nadir of <500 cells/microL). The choice of antibiotic for neutropenic fever is per the treating physician and the institution's hospital policy.

Dose modifications for fever are provided in **Table 4**. Antipyretic use is permitted for symptomatic relief of fever. In the absence of severe neutropenia, the use of antibiotics is at the clinical discretion of the examining physician/investigator. For complicated fever, defined as Grade ≥ 3 fever or any grade with signs and symptoms including; rigors, dehydration, hypotension, dizziness or weakness, the administration of both Dabrafenib and Trametinib should be interrupted/held.

Dose modifications for rash and general recommendations for rash management are provided in **Table 5**.

Dose modifications for hand foot skin reaction (HFSR) are provided in **Table 6**. Treatment of squamous cell carcinoma (SCC), keratoacanthoma (KA), and actinic keratosis (AK) lesions should be based upon institutional practice. Dose interruptions or modifications are usually not required for SCC/KA. Biopsies of any new skin lesions suspicious for malignancy and pre-malignancy (SCC, AK, KA) are recommended.

Dose modifications for renal insufficiency are outlined in **Table 7**.

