7.1. Expected Adverse Events for Dabrafenib (BRAFi)

Presented below are AEs considered related to dabrafenib treatment, observed in subjects with unresectable and metastatic melanoma treated with dabrafenib (150 mg BID), including subjects in BREAK-2 (data cut-off 7 July 2011), BREAK-MB (data cutoff 28 November, 2011), the randomized arm of BREAK-3 (data cut-off 19 December 2011), the monotherapy arm of BRF113220 (data cut-off 1 September 2011), and specific cohorts in the first-time-in-human study BRF112680 (data cut-off 25 March 2011). The total number included in this analysis is 578 subjects. Approximately 30 % of patients received treatment with dabrafenib for more than 6 months. Adverse reactions are listed below by MedDRA body system organ class and by frequency. The frequency categories used are:

Very common: $\geq 1/10$ ($\geq 10\%$)

Common: $\geq 1/100$ and $<1/10$ ($\geq 1\%$ and $<10\%$)

Uncommon: $\geq 1/1,000$ and $<1/100$ ($\geq 0.1\%$ and $<1\%$)

Rare: $\geq 1/10,000$ and $<1/1,000$ ($\geq 0.01\%$ and $<0.1\%$)

Table 11. Adverse Events for Dabrafenib (BRAFi) as monotherapy

| MedDRA SOC | Preferred Term |
|--|---|
| Neoplasms benign and malignant (including cysts and polyps) | Very Common: Skin papilloma, papilloma Common: Squamous cell carcinoma (SCC), including SCC of the skin and SCC in situ (Bowen's disease) and keratoacanthoma Acrochordon (skin tags) Seborrheic keratosis Uncommon: New primary malignant melanoma or other non-skin type malignancies. |
| Blood and the lymphatic system disorders | Very Common: Anemia Common: Leukopenia, Neutropenia |
| Vascular disorders | Uncommon: Venous thromboembolism, Pulmonary Embolism |
| Immune System Disorders | Uncommon: Hypersensitivity |
| Metabolism and nutrition disorder | Very Common: Decreased appetite Common: Hypophosphatemia |
| Nervous system disorders | Very Common: Headache Rare: Encephalopathy |
| Eye Disorders | Uncommon: Uveitis |
| Respiratory, thoracic and mediastinal disorders | Very Common: Cough |
| Gastrointestinal disorders | Very Common: Nausea, Vomiting, Diarrhea Common: Constipation, Gastrointestinal Bleeding, Peptic Ulcer, Gastrointestinal Ulcer Uncommon: Pancreatitis |
| Skin and subcutaneous tissue disorders | Very Common: Skin effects (rash, hyperkeratosis) Alopecia, Palmar-plantar erythrodysesthesia syndrome Common: Skin effects (Actinic keratosis, Skin lesion, Dry skin, Erythema) |

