| Eye Disorders | Common: Periorbital oedema, Vision blurred, Visual impairment Uncommon: Retinal Pigment Epithelial Detachment (RPED), Papilloedema, retinal vein occlusion, retinal detachment |
| Gastrointestinal disorders | Very Common: Dry mouth, Diarrhea, Nausea, Vomiting, Constipation, Abdominal pain Common: Stomatitis, Gastrointestinal Bleeding, Peptic Ulcer, Gastrointestinal Ulcer |
| Skin and subcutaneous tissue disorders | Very common: Alopecia, Rash (macular, maculopapular, erythematous or pruritic), Dermatitis acneiform rash, Pruritus, Dry skin Common: Erythema, palmar-plantar erythrodysesthesia syndrome, skin chapped, skin fissures |
| Musculoskeletal, connective tissue and bone disorders | Common: Blood creatinine phosphokinase increased (CPK) increased |
| General disorders and administration site conditions | Very Common: Fatigue, peripheral edema, Pyrexia Common: Asthenia, Facial edema, Mucosal inflammation |
| Infections and infestations | Common: Cellulitis, Folliculitis, Paronychia, Rash pustular |

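### Section 6.2 lets the dabrafenib rules prevail on Arm B and does not exempt visual changes, so its wording conflicts with the trametinib eye rules in 6.2.2

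*Combined protocol and SAP*

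**What the plan says.** The opening paragraph of Section 6.2 does four things.

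- It gives its reason: "Given that there are several overlapping AEs between Dabrafenib and Trametinib".
- It sets a general rule that dose modification and stopping "guidelines for all patients on ARM B must follow guidelines for Dabrafenib", and that trametinib is reduced, held or continued by similar criteria in those categories.
- It sets precedence: "If there is discrepancy between two guidelines for a given AE, please follow guidelines for Dabrafenib for patients on ARM B".
- It lists exceptions: "Diarrheas, peripheral/periorbital edema, acneiform rash, please follow guidelines given in section 6.2".

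Section 6.2 then gives trametinib dose rules for four specific toxicities: edema (Table 9), rash (Table 10), diarrhea (6.2.1) and visual changes (6.2.2). Sections 6.2.3 to 6.2.5 cover supportive care only. The exception list reflects the first three sets of dose rules and not the fourth.

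On the dabrafenib side, Section 6.1.1 says Table 2 is for "management of toxicities associated with the study treatment other than those pertaining to neutropenia, fever, rash" and several further named items. Eye events are not among the named items.

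**The concern.** A list that names three of four trametinib-specific rule sets can be read as deliberate. A site that takes the precedence sentence at face value would look for the dabrafenib rule on an eye event, find no eye-specific dose rule in Section 6.1, and fall back on the general Table 2. In the cases that matter, Table 2 is the more permissive of the two.

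The stake is patient safety. Trametinib could be continued or restarted in a patient for whom 6.2.2 requires a stop or an interruption, and two sites could dose the same event differently. Arm A patients who cross over to Arm B come under the same paragraph.

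**Working it through.** The plan states no figure on this point. The main check is a comparison of texts, followed by a short calculation of how often the events might occur.

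**Step 1: does Table 2 reach trametinib at all?** Every row of Table 2 doses dabrafenib, and every rule in 6.2.2 doses trametinib. Taken alone, the two can both be followed: continue one drug, stop the other. A conflict arises only through Section 6.2, which carries the dabrafenib criteria over to trametinib. The comparison below assumes that carry-over.

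**Step 2: the rules side by side.**

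| Event | Table 2, carried over to trametinib | Section 6.2.2 |
|---|---|---|
| RVO, Grade 1 | Continue at full dose | Permanent stop |
| RVO, Grade 2 | Consider holding | Permanent stop |
| RVO, Grade 3 | Hold, then reduce one level | Permanent stop |
| CSR, Grade 1 | Continue at full dose | Interrupt, then reduce one level |
| Any Grade 2 visual change | Consider holding | Interrupt at once |
| Any Grade 4 visual change | Discontinue, with restart possible if recurrence is judged unlikely | Permanent stop |

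There is no conflict for Grade 1 changes clearly not retinal or clearly unrelated to study drug. Grade 3 changes without RVO are handled in broadly the same way. The uveitis footnote to Table 2 requires an ophthalmology consult for symptoms such as blurry vision but sets no dose, so it neither adds to nor removes the conflict.

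**Step 3: does the text confine the paragraph to shared events?** If it did, RVO and CSR would fall outside it, because the only eye entry for dabrafenib in Table 11 is "Uncommon: Uveitis". Two features leave the question open.

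- Edema is exempted although Table 11 does not list it for dabrafenib. It appears for trametinib in Table 12: "Very Common: Fatigue, peripheral edema, Pyrexia", and in the eye row "Common: Periorbital oedema, Vision blurred, Visual impairment". If events not shared by both drugs were already outside the paragraph, the edema exemption would be unnecessary. Periorbital edema is exempted, while the two visual terms beside it in that row are not.
- Blurred vision appears in guidance for both drugs: the Table 2 uveitis footnote and the Table 12 eye row. A patient with undiagnosed Grade 2 blurred vision fits both sets of rules.

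**Step 4: expected events.** Inputs are 26 patients on Arm B (Section 13.2) and the frequency bands in Table 13. Patients are treated as independent. Upper ends are not reached, because each band stops short of its upper limit.

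Expected number = n × p; chance of at least one = 1 − (1 − p)^n.

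- RVO, uncommon (0.1% to under 1%), n = 26: 26 × 0.001 = 0.026 to under 26 × 0.01 = 0.26 events. Chance: 1 − 0.999^26 = 2.6% to under 1 − 0.99^26 = 23.0%.
- RVO, n = 52 (if every Arm A patient crossed over): 0.052 to under 0.52 events. Chance: 1 − 0.999^52 = 5.1% to under 1 − 0.99^52 = 40.7%.
- Chorioretinopathy, common (1% to under 10%), n = 26, assuming this term corresponds to the CSR of 6.2.2: 0.26 to under 2.6 events. Chance: 1 − 0.99^26 = 23.0% to under 1 − 0.90^26 = 93.5%.

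Table 13 marks RVO as not observed in Part C subjects given this combination dose; its listing rests on monotherapy data.

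**The case against.** The strongest reply is that the protocol, read as a whole, already makes 6.2.2 the rule for eye events. The 6.2 paragraph is introduced by overlapping events, and RVO is not in dabrafenib's Table 11. Section 6.1 opens by sending Arm B readers to 6.2 as well. Footnote k to the study calendar, which covers patients randomized or crossed over to Arm B, points to 6.2.2 for the visual stopping criteria. Section 5.5 ends treatment when any stopping criterion in Section 6 is met. Trametinib is given only on Arm B, so an override would leave 6.2.2 with almost nobody to govern. Two of the three exemptions also fit the narrow reading: diarrhea is listed for both drugs, and acneiform rash is a form of rash, which is shared and has its own dabrafenib table (Table 5).

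Most of this stands. A reader might infer that the protocol permits trametinib after RVO; the documents do not support that, and the intent runs the other way. But none of these provisions changes the precedence sentence, and Step 3 shows that its scope is not settled by its own words.

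Safeguards also count. Known RVO or CSR and predisposing findings are excluded (3.2.10, 3.2.11), and all patients have a baseline eye exam. Section 6.2.2 has RVO reported as an SAE, and 7.5.2 requires SAE reports within 24 hours. These lower the risk but do not set the trametinib dose for a new event, and 6.2.2 has no matching SAE instruction for CSR.

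**Conclusion.** The point holds as a conflict in safety wording that should be corrected. Section 6.2 states a precedence rule that, applied literally, weakens mandatory trametinib stops for RVO at Grades 1 to 3 and any Grade 4 visual change, and interruptions for CSR at Grade 1 and any Grade 2 change. The rest of the protocol indicates that this is not intended.

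Few RVO events are expected. The calculation assumes that the listed frequencies, which come from other studies, carry over to these patients, and the chorioretinopathy figure also rests on the assumed match with CSR. A reader might take that second range as a ceiling on the number of conflicts. It is not one: it uses 26 patients rather than up to 52, and it leaves out blurred vision and visual impairment. Nor does every such event produce a conflict, and the documents give no grade split. All these figures describe how often events occur; nothing in the documents shows how often a site would misread 6.2.

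The primary endpoint, power and decision rule are not affected.

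**What to change.** Add visual changes to the exception sentence in Section 6.2, for example: *Diarrhea, peripheral or periorbital edema, acneiform rash and visual changes (6.2.2) are managed under Section 6.2, whatever the dabrafenib tables provide.* Send sites a short notice. The sponsor's medical team should confirm that 6.2.2 is the intended rule, as footnote k implies. A separate statement on crossover is optional, because Section 4.3 has these patients re-registered on crossing to Arm B and footnote k already names them.

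The cost is one phrase and a site notice, with no added procedures, patients or time.
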